12.10 ECOG Performance Status

ECOG performance status will be assessed at Screening, and Week 3 (Day 17+-2 days) at Cycles 1-4, Day 1 of Cycles 5+, and 28 days Safety Follow-up. The ECOG performance status categories (6-point scale) are as follows:

| Grade | ECOG |
|--------------|---|
| 0 | Fully active, able to carry on all pre-disease performance without restriction. |
| 1 | Restricted in physically strenuous activity but ambulatory and able to carry out work of a light or sedentary nature, e.g., light housework, office work. |
| 2 | Ambulatory and capable of all selfcare but unable to carry out any work activities. Up and about more than 50% of waking hours |
| 3 | Capable of only limited self-care, confined to bed or chair more than 50% of waking hours |
| 4 | Completely disabled. Cannot carry on any self-care. Totally confined to bed or chair |
| 5 | Dead |

ECOG will be summarized by dose cohort using shifts from screening to the subject’s “worst” (i.e., highest number) ECOG score during the post-baseline study period and the last ECOG score taken post-baseline.

ECOG assessments will be included in subject listings.

12.11 Echocardiogram (ECHO) or Multigated acquisition (MUGA)

From the ECHO or MUGA scans, the LVEF (%) results are reported for the following time points:

- Screening.
- Treatment: An ECHO or MUGA scan (whichever was performed during screening) should be reported for 7 days from Cycle 3 Day 1, Cycle 5 Day 1 and Day 1 of every cycle thereafter

- Safety Follow-Up: An ECHO or MUGA scan (whichever was performed during screening) should be reported for the Safety Follow-Up visit if not performed in the previous 14 days.
- Long Term Follow Up (if applicable): An ECHO or MUGA scan (whichever was performed during screening) should be reported for each Long-Term Follow-Up visit.

Ejection Fraction percentages, LVEF (%), will be provided in table format by timepoint and by change from baseline summaries using descriptive summary statistics (n, mean, SD, median, range).

ECHO or MUGA test results to assess left ventricular ejection fraction (LVEF) will be presented in the subject listings.

12.12 Physical Examination

A physical examination should include a review of the following body systems: constitutional, skin, HEENT (head, eyes, ears, nose, and throat), neck, chest and lungs, cardiovascular, abdomen, neurological, and musculoskeletal, and genitourinary and gynecologic if indicated by the Investigator.

Symptom directed examinations should include an examination of organ systems related to subject symptoms for potential AEs. Any new post-baseline abnormal physical examination findings assessed as clinically significant should be recorded as an AE or SAE.

Physical examinations results will be displayed in subject listings.

12.13 Pregnancy Test

Individual subject data listings will be displayed for pregnancy test results.

13. PHARMACOKINETIC (PK) ANALYSIS

PK data analysis will be performed by the Shasqi R&D group and/or sponsor PK consultant and is not part of this SAP.

14. BIOMARKER ANALYSIS

Biomarker data analysis will be performed by the Shasqi R&D group and/or sponsor consultant and is not part of this SAP.

15. COMMITMENT TO GOOD STATISTICAL PRACTICE

15.1 Definition of Good Statistical Practice

International Conference on Harmonisation (ICH) Guidance on Statistical Principles for Clinical Trials (ICH E9) implicitly defines good statistical practice. Good statistical practice includes both appropriate statistical designs to minimize bias and to maximize precision of analysis plus operational excellence to assure credibility of results. The scientific design associated with any clinical trial is found in the protocol and in a more detailed pre-specified statistical analysis plan such as this one.

15.2 Data Management and Use of CDISC Standards

Data standards for clinical development of drugs have been defined and are maturing under various initiatives through the Clinical Data Interchange Standards Consortium (CDISC).

Shasqi will use third party vendors for clinical data collection and data analysis. Clinical data will be managed by Novotech (Australian based CRO), and will be captured in electronic case report form (eCRF) by the Medidata RAVE platform. The “raw” data contained in the eCRF clinical database will then be converted into Study Data Tabulation Model (SDTM) datasets per CDISC standards by Novotech. The SDTM datasets will then be utilized in statistical data analysis as the source to create Analysis Data Model (ADaM) datasets. These ADaM data conversions and data analysis will be conducted by Vantage Data Designs.

Other applicable standards include regulatory guidance's from the Food and Drug Administration (FDA), ICH Guidance on the Structure and Content of Clinical Study Reports (ICH E3), and ICH Guidance for Good Clinical Practice (ICH E6).

15.3 Testing/Validation Plan and Software System

Statistical Analysis Software (SAS) version 9.4 or later will be used to analyze the data, create summary tables, subject data listings, and graphical representation of the data. All SAS computer programs will be validated using industry standard validation procedures including independent quality control programming.

16. STATISTICAL ANALYSIS CHANGES FROM THE PROTOCOL

The analyses described are based on the final clinical study protocol SQ3370-101 Amendment 7 dated July 25, 2022. This SAP supersedes the statistical considerations identified in the protocol. The following table summarizes changes in the SAP versus the protocol:

| SAP | Protocol | Reason |
|-----|----------|--------|
| N/A | N/A | N/A |

18. SCHEDULE OF ASSESSMENTS

Phase 1 Dose Escalation, Cycles 1-4

| | | Screening | | Cycles 1 - 4 Treatment | | | |
|------------------|-------------------------------|--------------------|----------------------------|------------------------|-----------------|-----------------------------------|----------------|
| Study Day | Day -28 to Day -1 | Day 1 ^K | Day 2 / 3 / 4 | Day 5 | Day 10 ± 2 days | Day 17 ± 2 days | |
| | | Week 1 | | | Week 2 | Week 3 | |
| | | On-Site | On-Site | On-Site | On-Site | Telephone or On-Site ^A | On-Site |
| Screening | Informed consent ^B | X | | | | | |
| | Medical history | X | | | | | |
| | Review Inc/Exc Criteria | X | | | | | |
| | Confirm Eligibility | | X | | | | |
| Safety | Physical Exam | X | | | | | |
| | Symptom-Directed PE | | X ^C | | | | Cycle 1 only |
| | Vital Signs | X | X | X | X | | X |
| | ECHO or MUGA | X | Cycle 3 only ^D | | | | |
| | Triple 12-Lead ECG | X | X ^{C, E} | Cycle 1 only | Cycle 1 only | | Cycle 1 only |
| | ECOG | X | | | | | X |
| | AE Review | | X | X | X | X | X |
| | Conmed Review | X | X | X | X | X | X |
| Labs | Hematology & Chemistry | X | X ^C | Cycle 1 only | X | Cycle 1 only ^C | X ^C |
| | Coagulation & Urinalysis | X | | | | | X ^C |
| | Pregnancy Test | X ^F | X | | | | |
| | Serology | X | | | | | |
| | Plasma PK | | X | X | X | | |
| | PBMC | | Cycle 1, 2, 3 only | | | | |
| | Tumor Biopsy ^G | | X ^J | | | | |
| Tumor Evaluation | CT / MRI & RECIST | X | Every 6 weeks ^D | | | | |
| IP ^H | Administer SQL70 Biopolymer | | X | | | | |
| | Administer SQP33 Protodrug | | X ^I | X | X | | |

Investigator can perform unscheduled labs, ECGs and physical exams as needed / clinically indicated.

Notes:

A - Day 10 visit may be performed via telephone (using a lab closer to a patient's home) or on-site.

B - Written informed consent must be obtained prior to any study-specific procedures.

C - May be performed up to 3 days before the visit.

D - May be performed up to 7 days prior to projected every 6 weeks from C1D1 date.

E - ECG to be performed pre and post dose.

F - To be collected ≤ 7 days prior to Cycle 1 Day 1 for women of child-bearing potential.

G - Collect biopsy unless the tumor is considered too small to be biopsied; optional biopsy at Cycle 4 per investigator discretion
 H - IP administration is the last procedure for each visit (aside from post-dose vitals, ECG, and PK draws).
 I - SQP33 protodrug infusion occurs within 2 hrs ± 30 mins after receiving SQL70 biopolymer injection.
 J - Biopsy can be performed during screening and up to 4 days prior to Day 1 for other cycles
 K - Day 1-5 is typically Monday through Friday, however if the site can accommodate protocol procedures on the weekends Day 1 may start on any day of the week.

Phase 1 Dose Escalation, Cycles 5+, Safety Follow Up and Long Term Follow Up.

| | | Cycles 5+ Treatment | | | SFTY FU | LTFU |
|------------------|-----------------------------|----------------------------|---------------|---------|----------------------------------|---------------------------|
| Study Day | | Day 1 ^A | Day 2 / 3 / 4 | Day 5 | 28-34 days after last dose of IP | every 12 weeks (± 7 days) |
| | | On-site | On-site | On-site | On-site | Variable ^J |
| Safety | Symptom-Directed PE | X ^B | | | X | |
| | Vital Signs | X | X | X | X | |
| | ECHO or MUGA | X ^C | | | X ^I | |
| | Triple 12-Lead ECG | X ^{B, D} | | | X | |
| | ECOG | X ^B | | | X | |
| | AE Review | X | X | X | X | |
| | Conmed Review | X | X | X | X | |
| Labs | Hematology & Chemistry | X ^B | | X | X ^B | |
| | Coagulation & Urinalysis | X ^B | | | X ^B | |
| | Pregnancy Test | X ^B | | | X ^B | |
| | Optional Tumor Biopsy | X ^H | | | X ^J | |
| Tumor Evaluation | CT / MRI & RECIST | Every 6 weeks ^E | | | X ^K | X ^M |
| IP ^F | Administer SQL70 Biopolymer | X | | | | |
| | Administer SQP33 Protodrug | X ^G | X | X | | |
| Survival | Vital Status ^L | | | | | X |

Investigator can perform unscheduled labs, ECGs and physical exams as needed / clinically indicated

Notes:

A - Day 1-5 is typically Monday through Friday, however if the site can accommodate protocol procedures on the weekends Day 1 may start on any day of the week.

B - May be performed up to 3 days before the visit.

C - May be performed up to 7 days before the visit.

D - ECG to be performed pre and post dose.

E - May be performed up to 7 days prior to the projected every 6 weeks from C1D1 date.

F - IP administration is the last procedure for each visit (aside from post-dose vitals and ECG).

G - SQP33 protodrug infusion occurs within 2 hrs ± 30 mins after receiving SQL70 biopolymer injection.

H - Optional biopsy per investigator discretion; can be performed up to 4 days prior to Day 1.

I - ECHO or MUGA not required at the Safety Follow-Up visit if performed in the previous 14 days.

J - Optional tumor biopsy if the patient only completed one cycle, as second biopsy for comparison

will not be collected at Cycle 2.

K - CT / MRI & RECIST not required at the Safety Follow-Up visit if performed in the previous 6 weeks.

L – for up to 2 years after treatment end; collected during routine clinic visits, telephone or e-mail with the subjects/caregivers or referring physician offices.

M – Until disease progression per RECIST; May be performed up to 14 days before the visit

19. CTCAE TOXICITY LABORATORY GRADING CHART

| Panel | Analyte | Type | Standard Unit | Directional Change of Interest | Toxicity Grades (CTCAE v5.0) |
|------------|------------------|----------------------------|-------------------------|--------------------------------|--|
| Hematology | WBC count | WBC with differential | 10 ⁹ /L | Decrease | Grade 0: ≥ LLN Grade 1: < LLN – 3.0 × 10 ⁹ /L Grade 2: < 3.0 – 2.0 × 10 ⁹ /L Grade 3: < 2.0 – 1.0 × 10 ⁹ /L Grade 4: < 1.0 × 10 ⁹ /L |
| Hematology | ANC | WBC with differential | 10 ⁹ cells/L | Decrease | Grade 0: ≥ LLN Grade 1: < LLN – 1.5 × 10 ⁹ /L Grade 2: < 1.5 – 1.0 × 10 ⁹ /L Grade 3: < 1.0 – 0.5 × 10 ⁹ /L Grade 4: < 0.5 × 10 ⁹ /L |
| Hematology | Lymphocyte count | WBC with differential | 10 ⁹ cells/L | Decrease | Grade 0: ≥ LLN Grade 1: < LLN – 0.8 × 10 ⁹ /L Grade 2: < 0.8 – 0.5 × 10 ⁹ /L Grade 3: < 0.5 – 0.2 × 10 ⁹ /L Grade 4: < 0.2 × 10 ⁹ /L |
| Hematology | Hemoglobin | Erythrocytes and Platelets | g/L | Increase | Grade 0: ≤ ULN Grade 1: > 20 g/L + ULN Grade 2: > 20 – 40 g/L +ULN Grade 3: > 40 + ULN Grade 4: Not defined |
| | | | g/L | Decrease | Grade 0: ≥ LLN Grade 1: < LLN – 100 g/L Grade 2: < 100 – 80 g/L Grade 3: < 80 Grade 4: Not defined |
| Hematology | Platelet count | Erythrocytes and Platelets | 10 ⁹ /L | Decrease | Grade 0: ≥ LLN Grade 1: < LLN – 75 × 10 ⁹ /L Grade 2: < 75 – 50 × 10 ⁹ /L Grade 3: < 50 – 25 × 10 ⁹ /L Grade 4: < 25 × 10 ⁹ /L |

LLN=lower limit of normal. ULN=upper limit of normal.

The LLN and ULN for each analyte will be determined from the normal range of the local laboratory facility.

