12.7.1 CTCAE Grading

For the hematology laboratory tests of interest where CTCAE [version 5.0] severity criteria are specified, CTCAE severity grades will be assigned. These laboratory tests include:

| Panel | Test | CTCAE grade directions |
|--------------|-------------|-------------------------------|
| Hematology | ANC | Decrease |
| | Hemoglobin | Decrease / Increase |

| | | |
|--|------------------------------|----------|
| | Platelet Count | Decrease |
| | White Blood Cell (WBC) count | Decrease |
| | Lymphocyte Count | Decrease |

Analyses will be performed using “shift tables” of CTCAE toxicity grades relative to the baseline (pre-treatment) toxicity grade. The number and proportion of subjects with directional shifts of the “worst” CTCAE toxicity grade post-baseline and CTCAE toxicity grade of the last post-baseline visit relative to the baseline (pre-treatment) toxicity grade will be summarized for the selected hematology and chemistry parameters.

The CTCAE toxicity grading algorithms for the appropriate laboratory analytes are detailed in Section 19.

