12.7.1 CTCAE Grading

For the hematology laboratory tests of interest where CTCAE [version 5.0] severity criteria are specified, CTCAE severity grades will be assigned. These laboratory tests include:

| Panel | Test | CTCAE grade directions |
|------------|----------------|------------------------|
| Hematology | ANC | Decrease |
| | Hemoglobin | Decrease / Increase |
| | Platelet Count | Decrease |

| | | |
|--|------------------------------|----------|
| | White Blood Cell (WBC) count | Decrease |
| | Lymphocyte Count | Decrease |

Analyses will be performed using “shift tables” of CTCAE toxicity grades relative to the baseline (pre-treatment) toxicity grade. The number and proportion of patients with directional shifts of the “worst” CTCAE toxicity grade post-baseline and CTCAE toxicity grade of the last post-baseline visit relative to the baseline (pre-treatment) toxicity grade will be summarized for the selected hematology and chemistry parameters.

The CTCAE toxicity grading algorithms for the appropriate laboratory analytes are detailed in Section 19.

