19. CTCAE TOXICITY LABORATORY GRADING CHART

| Panel | Analyte | Type | Standard Unit | Directional Change of Interest | Toxicity Grades (CTCAE v5.0) |
|------------|------------------|----------------------------|-------------------------|--------------------------------|--|
| Hematology | WBC count | WBC with differential | 10 ⁹ /L | Decrease | Grade 0: \geq LLN Grade 1: $< \text{LLN} - 3.0 \times 10^9/\text{L}$ Grade 2: $< 3.0 - 2.0 \times 10^9/\text{L}$ Grade 3: $< 2.0 - 1.0 \times 10^9/\text{L}$ Grade 4: $< 1.0 \times 10^9/\text{L}$ |
| Hematology | ANC | WBC with differential | 10 ⁹ cells/L | Decrease | Grade 0: \geq LLN Grade 1: $< \text{LLN} - 1.5 \times 10^9/\text{L}$ Grade 2: $< 1.5 - 1.0 \times 10^9/\text{L}$ Grade 3: $< 1.0 - 0.5 \times 10^9/\text{L}$ Grade 4: $< 0.5 \times 10^9/\text{L}$ |
| Hematology | Lymphocyte count | WBC with differential | 10 ⁹ cells/L | Decrease | Grade 0: \geq LLN Grade 1: $< \text{LLN} - 0.8 \times 10^9/\text{L}$ Grade 2: $< 0.8 - 0.5 \times 10^9/\text{L}$ Grade 3: $< 0.5 - 0.2 \times 10^9/\text{L}$ Grade 4: $< 0.2 \times 10^9/\text{L}$ |
| Hematology | Hemoglobin | Erythrocytes and Platelets | g/L | Increase | Grade 0: \leq ULN Grade 1: $> 20 \text{ g/L} + \text{ULN}$ Grade 2: $> 20 - 40 \text{ g/L} + \text{ULN}$ Grade 3: $> 40 + \text{ULN}$ Grade 4: Not defined |
| | | | g/L | Decrease | Grade 0: \geq LLN Grade 1: $< \text{LLN} - 100 \text{ g/L}$ Grade 2: $< 100 - 80 \text{ g/L}$ Grade 3: < 80 Grade 4: Not defined |
| Hematology | Platelet count | Erythrocytes and Platelets | 10 ⁹ /L | Decrease | Grade 0: \geq LLN Grade 1: $< \text{LLN} - 75 \times 10^9/\text{L}$ Grade 2: $< 75 - 50 \times 10^9/\text{L}$ Grade 3: $< 50 - 25 \times 10^9/\text{L}$ Grade 4: $< 25 \times 10^9/\text{L}$ |

LLN=lower limit of normal. ULN=upper limit of normal.

The LLN and ULN for each analyte will be determined from the normal range of the local laboratory facility.

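### The hemoglobin-increase row of the CTCAE grading chart leaves values up to 20 g/L above ULN ungraded and lets Grade 1 overlap Grades 2 and 3, in both SAPs

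*SAP*

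**What the plan says.** Section 12.7.1 of each SAP lists the hematology tests that will receive CTCAE v5.0 grades. Hemoglobin is the only one graded in both directions, "Decrease / Increase". The same section says where the rule is found: "The CTCAE toxicity grading algorithms for the appropriate laboratory analytes are detailed in Section 19". It also says how the grades are used: "Analyses will be performed using “shift tables” of CTCAE toxicity grades relative to the baseline (pre-treatment) toxicity grade". The tables cover the worst post-baseline grade and the grade at the last post-baseline visit.

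For hemoglobin increase, Section 19 of the Phase 1 SAP sets Grade 0 at or below ULN and leaves Grade 4 undefined. The bands between are:

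- "Grade 1: > 20 g/L + ULN"
- "Grade 2: > 20 – 40 g/L +ULN"
- "Grade 3: > 40 + ULN"

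Section 19 of the Phase 2a SAP prints the same bands. Neither SAP gives another cut-off for hemoglobin increase, and the protocol (Appendix D) only links to CTCAE v5.0.

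**The concern.** A grading rule has to give every possible result exactly one grade. Here Grade 1 starts at the same point as Grade 2 instead of where Grade 0 ends, and it has no upper bound. That creates two separate faults: a gap just above ULN and an overlap higher up.

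Section 19 is the named specification for a planned output, so the row is not background text. Followed literally, it has these consequences:

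- A patient whose last value lies in the gap has no last grade.
- A patient whose baseline lies in the gap has no baseline grade to shift from.
- A patient whose highest value lies in the gap, with other values in the normal range, would show a worst grade of 0, because only the in-range values can be graded. The elevation would disappear from the table.
- In the overlap, the result depends on the order in which the conditions are coded. If grades are tested upward and the first match is taken, everything above ULN + 20 g/L becomes Grade 1, and Grades 2 and 3 are never assigned.

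**Working it through.** The plan has no computed figure to reproduce here. The check is whether the printed bands give each value one grade.

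**Inputs.** The four hemoglobin-increase bands in Section 19, which are the same in both SAPs. Let x = hemoglobin − ULN, in g/L. As printed:

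- Grade 0: x ≤ 0
- Grade 1: x > 20
- Grade 2: 20 < x ≤ 40
- Grade 3: x > 40

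**Test.** Apply these rules to values on both sides of each boundary. Then repeat with Grade 1 read as 0 < x ≤ 20.

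| x (g/L above ULN) | Grade(s) as printed | Grade with Grade 1 = more than 0 to 20 |
|---|---|---|
| −5 | 0 | 0 |
| 0 | 0 | 0 |
| 1 | none | 1 |
| 10 | none | 1 |
| 20 | none | 1 |
| 21 | 1 and 2 | 2 |
| 30 | 1 and 2 | 2 |
| 40 | 1 and 2 | 2 |
| 41 | 1 and 3 | 3 |
| 60 | 1 and 3 | 3 |

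**Gap.** Grade 0 stops at x = 0 and the next band opens above x = 20. The ungraded interval is 0 < x ≤ 20, so it is 20 − 0 = 20 g/L wide.

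**Overlap.** Grade 1 (x > 20) contains all of Grade 2 (20 < x ≤ 40) and all of Grade 3 (x > 40). Together those two bands cover every x > 20, so no value is Grade 1 alone.

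**Control.** The hemoglobin-decrease row was tested in the same way. Its Grade 1, "Grade 1: < LLN – 100 g/L", starts where Grade 0 ends. With an assumed LLN of 120 g/L (the SAPs use local laboratory ranges), the results were:

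| Hemoglobin (g/L) | 130 | 120 | 119 | 100 | 99 | 80 | 79 |
|---|---|---|---|---|---|---|---|
| Grade | 0 | 0 | 1 | 1 | 2 | 2 | 3 |

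Each value gets exactly one grade. The white cell, neutrophil, lymphocyte and platelet rows also start Grade 1 at the edge of Grade 0, so the fault is confined to the hemoglobin-increase row.

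**Which correction fits.** If the printed Grades 0, 2 and 3 stand, the only band that fills the space between Grade 0 and Grade 2 is more than 0 to 20 g/L above ULN. The last column of the first table shows that every tested value then has one grade. This follows from the chart alone and does not need the CTCAE text.

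**The case against.** The best defense is that the SAPs contain a chart, not code. The column is headed as CTCAE v5.0 grades, the protocol links to that source, and both SAPs (Section 15.3) promise independent quality-control programming. A programmer who meets the gap can look up the standard. Missing or wrong grades therefore follow only if the row is programmed literally. That qualification is fair. Even so, Section 12.7.1 names Section 19 as the algorithm, and two programmers could repair the row in different ways.

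The overlap is the weaker half of the point. Grading from the top down gives Grades 3 and 2 as presumably intended. The chart states no such precedence for a single value, though, and no precedence rule fills the gap.

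The row also decides little. Adverse event severity is graded by the investigator. Hemoglobin is also summarized as observed values and change from baseline, including the maximum post-baseline value, and out-of-range results are flagged in the listings. A high value would remain visible elsewhere. This stands, and it limits the weight of the point.

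A symbol could have been lost when the PDFs were read. That cannot be excluded completely, but it is unlikely: the same Grade 1 cut-off appears in two separate documents, and the inequality sign in the adjacent Grade 0 line survived. A look at the source files would settle it.

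Finally, the Phase 1 SAP is signed and marked final, so changing it is more than editing a cell. That is correct and is reflected in the fix.

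**Conclusion.** The error is real and is shown by the chart's own bands: a 20 g/L interval above ULN has no grade, and every value above ULN + 20 g/L satisfies two grades. It is minor. It affects only the hemoglobin-increase shift tables (worst grade and last grade) in the two SAPs. It does not affect anemia grades, the DLT definition, the Group 2 threshold for anemia and febrile neutropenia, or any sample size.

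Few patients are likely to be affected, since myelosuppression is the expected major toxicity. The documents do not allow a count. Elevations are not ruled out: eligibility sets a hemoglobin floor of 9.0 g/dL and no ceiling (protocol Section 4.1.1), and erythropoietin and, outside Phase 1 Cycle 1, transfusions are permitted (Section 5.9.1).

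The conclusion assumes that the row is applied as printed and that the PDF text is faithful. The corrected band also assumes that the printed Grades 0, 2 and 3 are as intended.

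**What to change.** In Section 19 of both SAPs, change Grade 1 for hemoglobin increase to more than 0 to 20 g/L above ULN (above ULN, up to and including ULN + 20 g/L). Check the whole row against the CTCAE v5.0 source before programming.

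- **Phase 2a SAP.** This is still marked Version 0.1, so the cost is one table cell before finalization.
- **Phase 1 SAP.** This is final and signed, and the Phase 2a SAP describes it as executed. The sponsor should confirm which cut-off was actually programmed. If the printed rule was used, the table should be rerun. In either case the correction should be recorded, through a SAP revision or in the clinical study report, where Section 1 of that SAP says deviations will be described. The cost is a short code check, a rerun of one table if needed, and a sentence of documentation.

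No new data are needed, and nothing changes in study conduct.
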